10.5 Registration

Participants will be registered into the trial once:

- a) Fully informed written consent has been obtained (and appropriately documented)
- b) Eligibility criteria have been fulfilled (and eligibility confirmed)
- c) baseline (0 day) assessments have been completed (at least seven days after the screening visit).

At this point participants will be assigned a registration number, made up of the letter R, the 3-digit site code and a 3-digit sequential number (RXXX-XXX). This number should be written on all samples and study documentation used from this point onwards.

10.6 Intervention

Upon registration into the research trial, participants will be self-taught to administer Anakinra on that day. Anakinra will be dispensed at baseline and at each clinic visit in accordance with the pharmacy manual, with each patient being provided with sufficient Anakinra to inject this once a day as per protocol. It is the responsibility of the PI or delegated research staff to inform the pharmacy department at their centre of impending registrations to ensure there is sufficient supply of the study drug.

10.7 Schedule for Assessments and Follow-up

All assessments and follow up are to be conducted in line with the Schedule of Assessments below: *Table 4: Schedule of Assessments:*

				Visit 1	Telephone follow up 1	Visit 2	Telephone follow up 2	Visit 3	Telephone follow up 3	Visit 4	Telephone follow up 4	Visit 5	Telephone follow up 5	
		Screening	Pre-baseline Telephone visit	Baseline^	Baseline +2wks	Day 30*	Day 30 +2wks	Day 60*	Day 60 +2wks	Day 90*	Day 90 +2wks	Time Point Day 120*	Day 180#	Premature Discontinuation
Proced	ures													
Signed Form	Consent	Х												
Registr	ation			Х										
Assess Eligibili	ment of ty Criteria	Х		Χ										
History	of Medical (including raphics)	Χ												
Review Concor Medica	mitant	Χ		Х	X	X	Х	Х	Х	Х	Х	Х	Х	х
(Daily a	ntervention after e to day			Х		Х		Х		Х		Х		
	Medical History and examinati on	Х										Х		X***
Clinical Assessment	CRPS History and Limb Examinat ion	Х										Х		X***
Clinical	Vital signs, weight, height, HR and BP	Х		Х		Х		X		Х		Х		X***
	Limb Volume	Х						Х				Х		
applica	or Blood	Х				Х		Х		х		х		
(CXR)	Radiograph and TB testing†	Х												

				Visit 1	Telephone follow up 1	Visit 2	Telephone follow up 2	Visit 3	Telephone follow up 3	Visit 4	Telephone follow up 4	Visit 5	Telephone follow up 5	
		Screening	Pre-baseline Telephone visit	Baseline^	Baseline +2wks	Day 30*	Day 30 +2wks	Day 60*	Day 60 +2wks	Day 90*	Day 90 +2wks	Time Point Day 120*	Day 180#	Premature Discontinuation
TB scre	ening skin test†	Х												
Issue and coll	pain diary lection	Х		Х		Х		Х		Х		Х		
Numerio Score Pain	cal rating for CRPS	Х	Х	X	×	X	X	X	X	X	X	Х	Х	Х
CRPS score	Severity			Х		Х		Х		Х		Х		
EQ5D-5	5L			X		Х		Χ		Х		Х	X	
PHQ-9				Х		X		Χ		Χ		Х		
HADS				X		X		Χ		X		X		
BPI				X		X		Х		Х		X		
Work S	tatus			Х								Х		
QST-bli unblinde				Х								X+		
Global of Chan	Impression ige											Х		
Assessi Adverse	ment of Events			Х	Х	Х	X	Х	Х	Х	Х	Х	Х	Х
Blood sample collection	Clinical Chemistr y/ Hepatic Function	X				Х		X		X		X		X
Blo	Haematol ogy	Х				Х		Х		Х		Х		х
Serology	HIV/Hep atitis B and C‡	х												
Researd	ch Blood	X			/ 6							X~		

Each Time point for follow up schedule can be +/- 3 days.

†unless a TB screen of either method listed has been done in the 3 months prior to the screening visit ‡unless a screen has been done in the 3 months prior to the screening visit

[^]Time between Screening and Baseline should be no more than 14 days.

^{*} Face to face appointment

^{**} Additional pregnancy tests may be conducted during the participation of the trial if there is any suspicion of being pregnant

^{***} Type of Clinical assessment will be only completed if at a visit. If completed by phone no clinical assessment will take place

[~] May be taken at earlier timepoint if participant withdraws before day 120.

⁺ unblinded QST

[#] Study Completion

All follow up visits will be scheduled from baseline (Day 0). Each participant will complete treatment administration from day 0 to day 120 and will be followed up for 180 days in total. During this time, scheduled follow ups will be conducted via both telephone as well as clinic visits. No face to face study visits are planned after 120 days.

Following registration each participant will be given a diary that they will fill in and record their pain intensity in accordance with the schedule:

- Weekly between day 0 to day 90
- Daily Between day 90 to day 120
- Weekly between day 120 to day 180

Clinic Follow-Up Visits:

Participants will need to attend clinics for follow-up at 30, 60, 90 and 120 days. These visits should be arranged at the baseline visit post registration. The following data should be collected and assessments/activities performed at all visits (unless specified differently below):

- Concomitant medication
- AEs
- Further Provision of Anakinra
- Collection of safety blood samples
- Collection of research blood samples (30ml, day 120 only)
- · Clinical assessment and examinations including:
 - o Pain assessment on NRS from their pain diaries
 - o Limb Volume (days 60 and 120 only)
 - o Vital signs: BP, HR, and weight

Telephone follow ups:

Research nurses (RNs) will telephone participants approximately 2 weeks (+/-3 days) after each clinic visit up to day 120 when the last drug dose is administered, and a final telephone follow up at day 180 at the end of the trial. Telephone appointments will be arranged and conducted by local research teams. The following information should be collected and recorded on the appropriate CRF:

- Concomitant medication
- AEs
- Pain assessment up to 120 days at the end of drug administration (NRS)
- EQ5D-5L questionnaire at day 180

Efficacy Assessments

This trial is not designed to determine efficacy, however data will be collected on outcomes that will be used to determine efficacy in a future definitive trial. Outcomes are detailed in section 9.

Safety Assessments

All AEs will be actively monitored from the time of consent, however, only those which are related to study procedures will be monitored between consent and the baseline visit. In addition, assessment of AEs will be made at each clinic visit (baseline (0 day), 30, 60, 90, 120 day and all post-clinic telephone visits (last telephone visit will take place on day 180 by a delegated research staff).

Blood sampling and monitoring (not including research bloods) will be performed at screening, 30, 60, 90 and day 120.

AE reporting is detailed in section 13.

Quality of Life Assessments

QoL will be measured by the EuroQol EQ5D-5L (baseline (0 day), 30, 60, 90, 120 and 180 day).

Health Economic Assessments

No formal health economic assessment will be made but work status will be noted on the CRFs.

Special Assays or Procedures

QST is performed at baseline and day 120 (detailed in Appendix 3. Quantitative Sensory Testing).

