13.6 Time Period for Active Monitoring of Safety Events

IMPORTANT: Any safety events occurring after the end of the below-described "active monitoring" period which meet the definition of serious (see section 13.2) and are recorded for this study (see section 13.1) must continue to be reported by sites to the LCTC in accordance with the timeframes and procedures described in section 13.12. The same processes established for SAEs within the active monitoring period should be followed for these events.

Active monitoring of safety events experienced by trial patients will be carried out from the time of trial consent. Between the point of consent and baseline (Day 0) only safety events which are related to trial procedures will be monitored. Thereafter all safety events will be monitored, beginning with the baseline visit (0 Day), then every 30 days at clinic visits, and at all telephone calls between clinic visits until the 120 day visit (end of treatment). Further safety events will be monitored at the end of the study on day 180 which is 60 days after the last dose of Anakinra.

Pregnant women will be followed up until a completed outcome of pregnancy (see Section 13.8 for more information on reporting pregnancy).

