14.4.3 Exposure to Treatment / Compliance

Exposure to treatment will be assessed by mean dose (mg) per participant. Dosing is once daily for a maximum of 120 days; the mean number of doses per participant over the treatment period (expressed as number of days treatment administered for) will be summarised.

Compliance of treatment will be captured by summarising the number of returned used syringes compared to non-used syringes.

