#### 25.2.3.2.2 CRPS severity score

#### 25.2.3.2.2.1 Derivation

The CRPS Severity score CRF collects the NRS pain score now and over the last 24 hours. The change in score will be calculated as the score at day 120 minus baseline score.

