25.2.3.2.7 BPI

25.2.3.2.7.1 Derivation

BPI is collected at baseline and days 30, 60, 90 and 120. A total of 9 questions are responded to in

regards to the pain experienced by each participant, questions 1,2, 7 and 8 will not be summarised.

Questions 3 to 6 summarise the pain experienced by the participant:

• At its worst in the last 24 hours

• At its least in the last 24 hours

On average

Right now

Each category is score 0 to 10 as 'No pain' to 'Pain as bad as you can imagine'.

Question 9 ask patients how, in the last 24 hours, pain interferes with:

General activity

Mood

Walking ability

Normal work (includes both work outside the home and housework)

Relations with other people

Sleep

Enjoyment of life

LCTC\_ST003\_TEMP1: SAP Template, V0.1, 08/01/2021 (developed using LCTC\_GE001\_TEMP4: LCTC Template of a Template, V1.0, 04/09/2020)

LIVERPOOL CLINICAL TRIALS CENTRE LCTC

Each category is score 0 to 10 as 'Does not interfere' to 'Completely interferes'. For question 9, the

average pain interference score will be calculated using the mean of the 7 categories responded to.

25.2.3.2.7.2 Analysis

The number of patients to complete the BPI form at each timepoint will be reported. Summaries will

be provided as in 25.2.3.2.2.2 for questions 3 to 6 and for the average pain interference score for

question 9. Continuous summaries will also be provided for scores at day 30, 60 and 90. Profile plots

will also be provided from baseline to day 120 for continuous data.

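### The ±3-day window lets Visit 5 fall on days 121 to 123, after the last dose on day 120, and the SAP summarises those values as day 120 with no rule for late visits

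*Protocol*

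**What the plan says.** **Visit window.** A note to Protocol Table 4 (section 10.7) states: "Each Time point for follow up schedule can be +/- 3 days". It covers every follow-up time point and does not treat Visit 5 separately.

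**End of dosing.** Section 10.7 says "Each participant will complete treatment administration from day 0 to day 120 and will be followed up for 180 days in total", and its telephone follow-up paragraph refers to calls "up to day 120 when the last drug dose is administered". Section 13.6 places the final safety contact "on day 180 which is 60 days after the last dose of Anakinra". Section 14.4.3 adds "Dosing is once daily for a maximum of 120 days". No text extends dosing to meet a late Visit 5.

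**Text that pulls against a late Visit 5.** Section 10.7 says "No face to face study visits are planned after 120 days", and section 13.6 equates the 120-day visit with the end of treatment.

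**What Visit 5 collects.** CRPS severity score, BPI, EQ-5D-5L, PHQ-9, HADS, global impression of change, QST, limb volume, work status and bloods. On recall, SAP 25.2.3.2.2.1 says "The CRPS Severity score CRF collects the NRS pain score now and over the last 24 hours". For the BPI, SAP 25.2.3.2.7 says "Question 9 ask patients how, in the last 24 hours, pain interferes with" a list of activities, and the worst-pain and least-pain items also cover 24 hours. EQ-5D-5L refers to the day of completion, PHQ-9 to two weeks and HADS to one week.

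**How the SAP labels these values.** They are day-120 values throughout SAP 25.2.3.2. For analgesic use, reaching day 120 is defined as having attended Visit 5. The SAP has no visit-window rule, no on-treatment flag and no sensitivity analysis for a Visit 5 held after the last dose.

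**The concern.** Dosing ends on a fixed study day, but the visit that measures the end-of-treatment state may float to either side of it. At days 30, 60 and 90 the same window is harmless because dosing continues on both sides. At day 120 it is not symmetric in meaning: a visit three days early is on treatment, and a visit three days late is not.

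For a fully adherent participant, whether the value is taken during or after dosing therefore depends on when the appointment was booked. The SAP then puts both kinds of value into one mean and SD. These outcomes are collected to help design a later randomised trial, so a mixture that is neither identified nor separable weakens their use for that purpose.

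**Working it through.** No sample-size or error-rate formula applies. The check is day arithmetic.

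**1. Last-dose day.** Protocol 13.6 puts day 180 at 60 days after the last dose: 180 − 60 = day 120. This reproduces the last-dose day in section 10.7.

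**2. Range of Visit 5.** 120 ± 3 gives days 117 to 123. Days 121, 122 and 123 lie after the last-dose day.

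**3. Position of each recall period.** Let gap = visit day − 120. A 24-hour recall starts at (visit day − 1). For a recall of L days, the share after the last-dose day is min(L, gap)/L when the gap is positive, and 0 otherwise.

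| Visit 5 held on | Gap (days) | 24-hour recall starts | PHQ-9 (L = 14) | HADS (L = 7) |
|---|---|---|---|---|
| 117 to 120 | −3 to 0 | before the last-dose day | 0 | 0 |
| 121 | 1 | on the last-dose day | 1/14 = 7% | 1/7 = 14% |
| 122 | 2 | 1 day after it | 2/14 = 14% | 2/7 = 29% |
| 123 | 3 | 2 days after it | 3/14 = 21% | 3/7 = 43% |

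**4. Reading by type of measure.**
- Same-day measures (EQ-5D-5L, QST, limb volume, pain now) are taken after the last-dose day on any of days 121 to 123.
- The 24-hour items start after the last-dose day on days 122 and 123. Day 121 is not clear-cut. On day 122 the recall may still overlap the final daily dosing interval by some hours, depending on injection time. Day 123 is beyond that interval.
- PHQ-9 and HADS are never wholly after dosing.
- Global impression of change asks about status since treatment started, so it has no short recall period to shift.

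**5. Outcomes that do not move with the visit date.** The primary outcome runs to day 180. Pain-intensity change uses diary days 93 to 120 (SAP 25.2.3.2.1.1). The SAP futility rule uses diary days 106 to 119 (SAP 25.1.2.4).

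**6. Sensitivity to the dose count.** Day 0 to day 120 inclusive is 121 daily doses, against a stated maximum of 120 days. If 120 doses are counted from day 0, the last falls on day 119. The largest gap is then 123 − 119 = 4 days, PHQ-9 reaches 4/14 = 29% and HADS 4/7 = 57%. Even an on-time day-120 visit is then one day after the last dose. The documents need to reconcile these two statements.

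**The case against.** **The protocol already ties the visit to the end of treatment.** Section 10.7 plans no clinic visit after day 120, section 13.6 treats the 120-day visit as end of treatment, and Table 4 ticks the intervention row at Visit 5. Section 10.7 also lists further drug supply under the clinic visits, and dispensing detail sits in a pharmacy manual that is not part of these documents. This shows the intent, but none of it alters the window. The last-dose day and the cap on dosing are explicit, so what remains is an unreconciled conflict.

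**The outcomes that matter most are unaffected.** Protocol 14.2 names change in pain NRS as the main outcome for planning later studies, and that comes from the diary. The rest are descriptive summaries in a trial that section 10.7 says is not designed to determine efficacy. This stands, and it limits the importance of the point.

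**Narrowing the window could harm the diary outcome.** Early visits leave the last diary days outstanding, and SAP 25.2.3.2.1.1 divides by a fixed 28 with no imputation. If three entries were never returned and the formula were applied as written, an illustrative true mean of 7 would become 7 × 25/28 = 6.25, a spurious fall of 0.75. The risk is real, but it already exists because days 117 to 119 are permitted now. Weekly diaries also run from day 120 to day 180 with no clinic visit in that period, so a return route after the last visit is already needed. The fix should name that route and correct the divisor.

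**Conclusion.** The point holds as a minor design and reporting gap. A completer's Visit 5 may fall up to three days after the last-dose day and still be summarised as day 120, and the window conflicts with sections 10.7 and 13.6. The exposure is confined to same-day measures on days 121 to 123 and 24-hour-recall items on days 122 and 123. PHQ-9 and HADS are partly affected, at most 21% and 43% of recall with a last dose on day 120.

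A reader might go further and infer that a large fraction of values are drug-free and that mean change is understated by that fraction. If visits were spread evenly over the seven permitted days, 3/7 (43%) would fall after day 120 and 2/7 (29%) on days 122 and 123. The documents do not support that inference. The window is a tolerance around a target of day 120, visits are to be arranged at the baseline visit, and nothing indicates an even spread. The documents show only that no dose is scheduled in those days; they give no figure for how fast any effect is lost. The direction and size of any distortion therefore cannot be computed.

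**What to change.** 1. **SAP.** For treatment completers, list the interval from last dose to Visit 5. Repeat the day-120 summaries of the same-day and 24-hour-recall outcomes without visits held after the last-dose day. This works even if the protocol can no longer be amended. It should need only visit and last-dose dates, assuming both are recorded for completers.
2. **Protocol 10.7, Table 4.** Reconcile the window with the statements in 10.7 and 13.6 so that Visit 5 is not scheduled after day 120. One option is −3/0 days for that visit (days 117 to 120), leaving ±3 days elsewhere.
3. **Diary.** State that entries up to day 120 are returned by the same route as the day 120 to 180 diary. In SAP 25.2.3.2.1.1, divide the daily mean by the number of completed entries, as the SAP already does for the futility rule.
4. **Dose count.** Reconcile day 0 to day 120 with the 120-day maximum, because the last-dose day fixes which visits count as late.

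The cost is a footnote change and a few SAP sentences. The downside is a shorter booking window for one visit, four permitted days instead of seven, and more diary days returned after the visit.

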9 OUTCOMES

Primary Outcome

The proportion of patients with no serious or condition-specific AE's. Pre-determined potential condition-specific AE's include persistent pain at injection site (greater than 1 week) of at least moderate intensity (5 or greater on a 0-10 NRS scale) and increase in CRPS associated pain (>=2points NRS), ongoing for >1 month.

Secondary Outcome(s)

To identify any barriers to patient recruitment and retention:

- 1. Monthly registration rate.
- 2. The proportion of patients completing the study retention rate, and reasons for non-completion.

To obtain data that will enable a larger RCT to be designed in the future:

- 3. Change of pain intensity measured on a 0-10 point NRS from baseline (0 day) to 4 months/120 days after completion of Anakinra administration. Pain intensity at 120 days is defined for the purpose of this study a mean of the weekly scores and daily over the last month of drug administration. This is determined by calculating the results of the patient pain diaries.
- 4. CRPS severity score
- 5. Global Impression of change
- 6. Analgesic Medication use
- 7. EQ-5D 5L
- 8. Patient Health Questionnaire 9 (PHQ-9)
- 9. Brief Pain Inventory (BPI)
- 10. Hospital Anxiety and Depression Scale (HADS)
- 11. Skin sensitivity measured by mechanical quantitative sensory testing (QST)
- 12. Limb Volume (Figure of 8)
- 13. Work status

Table 3: Timepoints for objectives and outcome measurements

Objectives	Outcome Measures	Timepoint(s) of evaluation
To determine the safety/tolerability of Anakinra	Proportion of patients without SAEs	Baseline (0 day) -180 days
To identify barriers to recruitment and	Monthly registration rate	Baseline (0 day)
retention	Retention rate (proportion of patients completing study) and reasons for non-completion	Day 120/180
To obtain data that will enable a larger RCT to be designed in the future	Change of pain intensity measured on a 10-point NRS	Baseline (0 day) – day 120
	CRPS Severity Score	Baseline (0 day), 30, 60, 90, 120 days
	Global Impression of change (PGIC)	Day 120
	Change in Pain Interference measures: PHQ-9, BPI and HADS	Baseline (0 day), 30, 60, 90, 120 days
	EQ5D-5L	Baseline (0 day), 30, 60, 90, 120 and 180 days
	Skin sensitivity measured by Mechanical QST	Baseline (0 day) and day 120
	Limb volume (by figure of 8)	Screening visit, 60 day and 120 days
	Work status	Baseline (0 day) and day 120
	Analgesic Medication use	Baseline (0 day) and day 120

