11 PROGRESSION CRITERIA

Monitoring for clinical trial progress will focus on recruitment and safety. This will be done by the IDSMC.

The following factors will be used to inform the decision to progress into the next stage of the trial:

- 1. **Recruitment**. Assessed 6 months from recruitment start. Initial recruitment rate of 0.5 participants each month per centre for the first 6 months from recruitment start.
- 2. **Safety**. Assessed 12 months from recruitment start (or later if it takes longer for 10 participants to be registered): For the first 10 registered participants, 3 or less reporting persistent pain (greater than 1 week) at injection site of at least moderate intensity (5 or greater on a 0-10 NRS scale) or substantial CRPS pain increase (>=2points NRS), ongoing for >1 month despite and from the time of pain-related treatment stop.
- 3. **Safety**. Assessed 12 months from recruitment start: Consider stopping if 30% or greater of study participants experiencing a serious adverse reaction (SAR).
- 4. **Recruitment and adherence**: At 12 months from recruitment start to have at least 12 participants registered and at least 50% of registered participants completing their active treatment.
- 5. **Futility**. After 12 participants have been recruited and completed 4 months treatment period, an average of no pain increase among completed participants (to visit 5/ 120 day) and at least one participant reporting at least 2 points of pain reduction on the NRS (rounded to the nearest whole number), both these criteria referring to the average pain recordings over the last two weeks before visit 5 / 120 day compared to baseline (0 day).

The IDSMC will use the above progression rules as a guide during regular monitoring with regards to trial progress and will provide a recommendation to the TSC concerning continuing the study. The above are not intended as strict stop/start criteria.

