#### 25.2.3.2.1.2 Analysis

Continuous data will be summarised using mean, SD, median, IQR, maximum and minimum value. Summaries will be provided for:

- Baseline score
- Average weekly scores (days 93 to 120)
- Daily average over the last month (days 93 to 120)
- Change in scores for weekly and daily average at day 120 from baseline.

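### Pain after the last dose (days 120 to 180) is recorded by participants, but the diary has no scheduled collection, the day-180 NRS is specified inconsistently, and the SAP plans no summary of pain scores after day 120

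*Protocol*

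**What the plan says.** **Recording.** After registration, Protocol 10.7 sets a weekly diary to day 90, a daily diary to day 120, and then "Weekly between day 120 to day 180".

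**Collection.** The Table 4 row for issue and collection of the diary is marked at screening, baseline and days 30, 60, 90 and 120. It is blank at day 180. The same section adds: "No face to face study visits are planned after 120 days".

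**NRS at the calls.** The Table 4 row for the CRPS pain NRS is marked at every contact, including the day-180 call. The telephone follow-up list in the same section gives "Pain assessment up to 120 days at the end of drug administration (NRS" and then names EQ-5D-5L at day 180.

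**Primary outcome.** Protocol section 9 counts a CRPS pain increase of 2 or more points lasting more than a month as a condition-specific event. Table 3 gives the safety window as "Baseline (0 day) -180 days".

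**SAP.** The pain-intensity derivation (25.2.3.2.1.1) uses diary days 93 to 120, and the last listed summary is "Change in scores for weekly and daily average at day 120 from baseline". Analgesic use (25.2.3.2.4) and EQ-5D-5L (25.2.3.2.5) are both summarised at day 180. Section 25.1.2.2 derives a substantial pain increase as pain at day X minus pain at day X-30, for X above 30 and with no upper limit. It says the yes/no answers and the derived result will both be used, and it names Form 7, the final telephone follow-up. Section 25.2.2.1 also lists Form 7 as a source for the primary outcome.

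**The concern.** For anyone who finishes the 120-day course, days 120 to 180 are the only time off drug. A pain increase after stopping can be seen only then, and it falls inside the primary outcome's window. Participants are asked to write down scores that would show it, yet no step brings those scores back and no analysis uses them. The text and the table also give sites different instructions about whether to ask for a pain score at day 180.

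Two things are at stake. One is how completely pain-increase events are found in the last third of follow-up. The other is information for the RCT. Protocol 14.2 names change in NRS pain as the main outcome feeding later studies, and what happens after the last dose bears on how long that trial should follow its participants.

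**Working it through.** The plan states no figure on this point, so there is none to reproduce. The check compares the schedule with what the SAP needs.

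1. **Table 4 rows.** The table has 13 contact columns. The diary row is marked in 6 of them, the last at day 120. The NRS row is marked in 13 of 13, including day 180.

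2. **Size of the uncollected record.** 180 - 120 = 60 days, and 60/180 = 33% of follow-up. Weekly entries counted from day 120 fall on days 127, 134, 141, 148, 155, 162, 169 and 176, which is 8 entries. With the planned 30 participants, 8 x 30 = 240 scores. This is an upper bound that assumes everyone completes treatment and makes every entry.

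3. **The SAP's derived increase after day 120.** The rule is pain(X) - pain(X-30).
   - At X = 180 it needs pain at 180 - 30 = day 150. No contact is scheduled between days 120 and 180, and the 3-day visit window does not help.
   - For X from 121 to 150, X-30 runs from 91 to 120, where daily diary scores exist. The score at X itself is only in the uncollected diary.
   - For X from 151 to 180, X-30 runs from 121 to 150, again only in the uncollected diary.
   - So for a completer the rule cannot be run at any day after 120 from data scheduled for collection.

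4. **With the diary collected.** Entries on days 127 to 148 pair exactly with daily scores on days 97 to 118. The day-180 NRS pairs with the day-148 entry at 180 - 148 = 32 days, which is close to the rule's 30.

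5. **Dating an increase.** To have lasted more than 30 days by day 180, an off-drug increase must have begun before day 150. Among the weekly entries, days 127, 134, 141 and 148 meet this (180 - 148 = 32), while day 155 does not (180 - 155 = 25). A single day-180 score cannot show on which side of that line the increase began.

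6. **What remains if Table 4 is followed.** One change per participant, NRS at day 180 minus NRS at day 120, can be derived. Its 95% confidence half-width is t(0.975, n-1)/sqrt(n) times the SD of the change:
   - n = 30: 0.37 SD
   - n = 24: 0.42 SD
   - n = 20: 0.47 SD

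   The documents give no SD, and 24 and 20 are assumed retention levels.

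**The case against.** The strongest reply is that section 10.7 opens by making Table 4 the governing schedule. Sites should then record the NRS at day 180, and a day 120 to day 180 change can be derived. That stands. A reader might infer from the telephone text that no pain score after the last dose will exist, but the documents do not support this. The two places conflict and need reconciling.

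A reader might also infer that the SAP ignores off-drug pain. It does not. Form 7 asks about pain-increase events and is listed as a source for the primary outcome, and EQ-5D-5L, which has a pain/discomfort item, is reported at day 180. The gap is in NRS scores and in the derived check that the SAP says will be used beside the yes/no answers.

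The sponsor could add that the pain-intensity outcome is defined at day 120 and that the SAP implements that definition. This is true, so the missing off-drug summary is an omission worth filling, not an error in that outcome.

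It is tempting to say that the on-to-off change would separate a drug effect from regression to the mean. It would not. Participants know when the drug stops, so expectation and natural fluctuation remain, and the protocol says the trial is not designed to determine efficacy.

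Nor should progression criterion 2 be cited for completers. Its clock, "ongoing for >1 month despite and from the time of pain-related treatment stop", refers to stopping because of pain, it covers the first 10 registrants, and participants who stop early stay on the visit and call schedule.

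Finally, the diary row covers issue as well as collection, so issue of the last diary at day 120 is scheduled. What is missing is a stated way to get it back.

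**Conclusion.** The concern holds in a limited form. The diary instruction, Table 4 and the telephone text do not agree on pain after day 120, and the SAP plans no summary of NRS pain in that period. If Table 4 is followed, one day-180 score and the Form 7 answers remain. The time course over 60 of 180 days cannot be reconstructed from scheduled data, and for completers the SAP's 30-day difference cannot be run at day 180. It should be corrected because the primary outcome runs through this period and the correction is cheap.

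This rests on four assumptions:
- The Table 3 window applies to the whole primary outcome, although that row names only SAEs.
- The pain-increase derivation in the SAP's progression section also serves the same event in the primary outcome.
- The Table 4 marks are read correctly from the extracted text. Both rows fit 13 columns.
- Form 7 holds no more than the SAP describes, since the form itself is not in the documents.

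**What to change.** 1. **Table 4:** add a day-180 collection point for the day 120 to 180 diary, either by reading the scores out at the existing call or by postal return.
2. **Telephone follow-up text in 10.7:** reconcile it with Table 4 so that the CRPS pain NRS is recorded at day 180, and confirm that Form 7 has a field for it.
3. **SAP 25.2.3.2.1:** add a descriptive summary of pain for days 121 to 180, with change from baseline and change from the participant's day 93 to 120 mean. Label it as supportive information for planning the RCT.
4. **SAP 25.2.2.1:** state that these scores are used alongside Form 7 when classifying CRPS pain increase up to day 180.

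The cost is a protocol wording change, a few minutes on a call already scheduled or a prepaid envelope, and one extra table. No visit or participant is added. The downside is that scores read out by telephone or posted may be less complete than diaries handed in at a visit, so the number of entries received should be reported with the summary.
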